3.2.2 Secondary Study Endpoints

Change in accuracy on additional language assessment given over baseline & follow-up visits will serve as secondary outcomes.

CONFIDENTIAL

3.2.3 Primary Safety Endpoints [if applicable]

The risks from language tasks and MRI imaging are minor. Data on adverse events occurring during the 4 weeks in which tDCS is being administered will be collected by asking subjects at the beginning and end of every session if they have noted any adverse effects or new symptoms since their most recent. Reports of adverse effects from tDCS and other aspects of the study (brain imaging, language tasks and mCILT) will serve as the primary safety endpoint.

4 Study Population and Duration of Participation

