NACC - National Alzheimer's Center Cohort

naPPA – non-fluent / agrammatic Primary Progressive Aphasia

NWRT – Non-word Repetition Test

svPPA – Semantic variant Primary Progressive Aphasia

tDCS – Transcranial Direct Current Stimulation

WAB: Western Aphasia Battery

WAB-AQ: Western Aphasia Battery – Aphasia Quotient

VAMC: Veteran Affairs Medical Center

Study Summary

Title	Using Transcranial Direct Current Stimulation to Reveal Mechanisms of Language Loss and to Treat Progressive Aphasia Associated with FTD and Related Dementias
Short Title	PPA DOD
IRB Number	843286
Phase	Phase 2
Methodology	Double-blind, sham controlled, crossover design
Study Duration	12 months
Study Center(s)	Single-center
Objectives	
Primary – Characterize tDCS treatment mechanisms by identifying responders to stimulation
 
Secondary – Reveal structural and functional brain connections that predict response to tDCS.

Number of Subjects	62

**Main Inclusion and
Exclusion Criteria**

*Between the ages of 45-80
Diagnosis of PPA
Native English Speaker
No additional neurological disease*

**Investigational
Product (drug,
biologic, device, etc.)**

**For Device include
the planned use** *We will be using a commercially available tDCS device manufactured by
NeuroConn.*

**For Drug, food,
cosmetic, etc.
include the dose,
route of
administration and
dose regimen** *Two 5x5 electrodes at 1.5 mA; anode=F7, cathode = O1.*

**Duration of
administration (if
applicable)** *Stimulation will take place over 2 weeks; 10 sessions for 20 minutes each.*

Reference therapy *Sham tDCS*

**Statistical
Methodology** *Linear Mixed Models will be used to compare the performance of subjects receiving real tDCS to subjects receiving sham tDCS on change in WAB-AQ scores.*

Safety Evaluations *Subject reports of adverse events will serve as the primary measure of safety.*

**Data and Safety
Monitoring Plan** *PI will oversee safety and data monitoring*

CONFIDENTIAL

This material is the property of the University of Pennsylvania.

BACKGROUND AND STUDY RATIONALE

This document is a protocol for a clinical research study. This study will be conducted in full accordance with all applicable University of Pennsylvania Research Policies and Procedures and all applicable Federal and state laws and regulations including US and international standards of Good Clinical Practice.

1. Introduction

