Primary Progressive Aphasia (PPA), a condition affecting 20-40% of patients with frontotemporal lobar degeneration (FTLD) disorders and a smaller proportion of patients with Alzheimer's disease (AD), is characterized by progressive deterioration of language function (Mesulam, 2001). There are currently three recognized variants of PPA: non-fluent/agrammatic, logopenic, and semantic. Non-fluent/agrammatic (naPPA) and logopenic (lvPPA) variant are both characterized by difficulties with speech-language production; naPPA typically involves grammatical simplification, effortful speech, and speech apraxia, while lvPPA is associated with phonological errors and poor word retrieval/repetition. Semantic variant PPA (svPPA) involves anomia, reduced expressive vocabulary, and single-word comprehension deficits (Gorno-Tempini et al., 2011). All forms of PPA profoundly impact communication ability and impose a significant burden on patients and their caregivers (Riedijk et al., 2006; Mioshi, et al., 2009; Diehl-Schmid et al., 2013; Mioshi et al., 2013). Speech and language therapies for PPA have shown positive but only modest results (Henry et al., 2008; Croot et al., 2009, 2015; Beeson, 2011; Jokel et al., 2014), and medications used to treat dementias are ineffective. Thus, development of new treatments that can reverse, arrest, or significantly slow language loss in persons with PPA would represent a tremendous step forward for those suffering from this debilitating condition.

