4.1 Inclusion Criteria

Study subjects must meet all of the following inclusion criteria:

- Presence of aphasia attributable to Primary Progressive Aphasia.
- Between the ages of 45 and 80.
- Must be a native English speaker

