4.2 Exclusion Criteria

- Cognitive impairment of sufficient severity to preclude them from participating in testing / therapy (MMSE < 15).
- History of seizures or unexplained loss of consciousness in the past 6 months
- Subjects with metallic objects in the face or head other than dental apparatus such as braces, fillings, and implants.
- Subjects with Pacemakers or ICDs.
- Subjects with previous craniotomy or any breach in the skull; skull defect could be associated with shunting of current leading to unpredictable location and level of current affecting the brain.
- Subjects with a history of stroke
- Subjects with history of TIA (at the PI's discretion, a TIA which occurred at least 6 months ago is okay if no other events have been observed)
- Subjects with a history of small vessel disease
- Use of sedation medication that may cause arousing the subject during testing difficult (must be free of meds that impair cognition for at least 3 months)
- Pregnancy

CONFIDENTIAL

This material is the property of the University of Pennsylvania.

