9.7 Stopping Rules

The trial maybe stopped for safety concerns or poor study performance, including failure to recruit and/or retain subjects. Subjects who report significant discomfort from tDCS, or worsening of language or cognition during tDCS will remain in the study with treatment discontinuation. Two sources of information about short-term adverse effects of tDCS on language function will be available. First, subjects and family will be asked if they see evidence of deterioration in language or other faculties each day they return for tDCS. Second, the researcher administering the mCILT will see the subject during each treatment session. S/he will be instructed to inform the PI if s/he observes a clinically significant worsening in language function. If the mCILT administrator is concerned, the WAB will be repeated. If this supports a decline from baseline (operationally defined as more than 5 points below baseline), the adverse effect will be reported and the subject will be withdrawn from treatment. In order to support the intention-to-treat analysis, all such subjects will be strongly encouraged to continue follow-up.

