12.2 Adequacy of Protection Against Risks

Behavioral Studies: To protect against fatigue subjects will be permitted to rest or discontinue testing at any time. Should subjects appear to be made anxious by the tasks, testing will be terminated. Subjects will be told that they are free to withdraw from the testing at any time. The PI is not aware of any significant adverse effect from behavioral testing of the type proposed in more than 30 years of work with brain-lesion subjects.

MRI Brain Imaging: No contrast agents will be administered. The major risk from MRI is that the strong magnetic field will dislodge a metallic object inside the subject's body (e.g., aneurysm clip) or interfere with an implanted device (e.g., cardiac pacemaker). Standard protocols have been developed at the University of Pennsylvania to ensure that subjects at risk do not undergo an MRI scan. This protocol includes an extensive checklist that is completed by the subject or family member; additionally, the MRI technician interviews subjects prior to entering the MRI suite. A second potential concern comes from loose metallic objects in the MRI suite that can serve as missiles if they are drawn to a powerful magnet. Metallic objects that are not secured to the floor or wall are not permitted in the MRI suite. We note that these procedures have been employed in the clinical and research settings at the University of Pennsylvania for many years; no adverse effects from MRI scanning have been experienced to date.

Participants with a documented history of claustrophobia or known issue with participating in an MRI (i.e. anxiety) may request the use of a sedative during the scans. The PI may prescribe a mild benzodiazepine to alleviate any discomfort (i.e. claustrophobia/anxiety) caused by the MRI. For safety purposes, the participant would not be allowed to travel home alone, and would be required to have a caregiver present to provide transportation. If a caregiver is not available, transportation will be arranged for them by our research staff.

The following steps will be taken to minimize risks from tDCS identified above:

1. We will use durations and stimulus intensities that fall within parameters that have been safely used throughout tDCS research.

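### The primary safety endpoint relies on people with progressive aphasia answering a general question, with no accessible or proxy route for the expected tDCS sensations, so these may be under-recorded.

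*Combined protocol and SAP*

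**What the plan says.** Section 3.2.3 states that adverse-event data for the stimulation weeks "will be collected by asking subjects at the beginning and end of every session if they have noted any adverse effects or new symptoms", and makes reports of adverse effects the primary safety endpoint. The Study Summary agrees: "Subject reports of adverse events will serve as the primary measure of safety".

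Aphasia is an entry requirement (4.1: "Presence of aphasia attributable to Primary Progressive Aphasia"). The introduction says that the semantic variant "involves anomia, reduced expressive vocabulary, and single-word comprehension deficits". It describes the other two variants as disorders of speech and language production, with poor word retrieval in the logopenic form. Section 4.5 plans 31 participants with svPPA and 31 with naPPA or lvPPA. Section 4.2 excludes cognitive impairment that rules out testing or therapy, marked by an MMSE below 15. It sets no minimum comprehension score.

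Other sections add safety information:
- 9.2: specific questioning at each contact, and examination where appropriate.
- 9.7: "subjects and family will be asked if they see evidence of deterioration in language or other faculties each day they return for tDCS". The mCILT administrator also watches for worsening language, and the WAB is repeated if there is concern.
- 12.2: monitoring for the listed tDCS effects during and after stimulation.
- 7.2: an examination if the participant reports new complaints or a change.

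**The concern.** Understanding a spoken, open question and then finding the words to answer draws on the abilities that PPA erodes. The commonest effects listed in 12.1 are sensations that only the participant can feel. A person who does not follow the question, or cannot name the sensation, may be recorded as having no event.

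The protocol allows for this difficulty elsewhere. Section 4.3 justifies a written e-mail script because people with aphasia often understand written information more easily. For MRI safety, 12.2 says "This protocol includes an extensive checklist that is completed by the subject or family member". Nothing comparable is described for the tDCS symptom question.

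At stake is whether the trial's tolerability rates can be taken at face value. Participants who cannot voice a problem may also not reach the steps in 7.2 and 12.2 that follow a report.

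**Working it through.** The plan states no event count, precision or power for safety, so there is no figure to reproduce. The check is mainly a comparison of sections, followed by an illustration.

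**Does another source cover the sensations in 12.1?**
- Family question (9.7): asks about decline in language or other faculties, not about burning, itching or tingling, headache or pain.
- mCILT administrator (9.7): looks for worsening language. During therapy a barrier blocks the view between participant and researcher, and the administrator is trained not to respond to nonverbal communication (5.2.1). That training concerns the therapy task, but no section says how nonverbal discomfort would be noticed or recorded.
- Specific questioning (9.2): still puts questions to the participant. Examination is only as appropriate.
- Examination (7.2) and ending a session (12.2): both start from the participant's report.
- Daily stimulation sheet (5.5): date, administrator, code and notes. No symptom list is named.

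Language or cognitive decline therefore has sources independent of self-report, and redness is visible. The subjective sensations have no described alternative route.

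**Is the question asked at one consistent time?** Section 3.2.3 says at the beginning and end of the session, 7.7 says before and immediately after tDCS, and 9.8.1 says during and immediately after. Sessions last 60 to 90 minutes with stimulation in the first 20 (5.2.1), so the end of the session falls 60 − 20 = 40 to 90 − 20 = 70 minutes after stimulation stops. These are different time points with different demands on recall.

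**Illustration of size.** Let *s* be the probability that a participant conveys a symptom that occurred. The documents give no value; 0.5 to 1.0 is assumed. Expected number recorded = 62 × rate × *s*, with the rates cited in 12.1 taken as true rates:

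| Effect (rate) | s = 1 | s = 0.9 | s = 0.7 | s = 0.5 |
|---|---|---|---|---|
| Itching/tingling (30%) | 18.6 | 16.7 | 13.0 | 9.3 |
| Burning (22%) | 13.6 | 12.3 | 9.5 | 6.8 |
| Headache (10%) | 6.2 | 5.6 | 4.3 | 3.1 |

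For a rarer effect, with an assumed true rate of 2%, the chance of recording at least one case is 1 − (1 − 0.02*s*)^62: 71%, 68%, 58% and 46% for the same values of *s*.

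If half the participants had *s* = 0.9 and half *s* = 0.5, overall *s* would be (0.9 + 0.5)/2 = 0.7. A true 30% would then be recorded as 27% in one half and 15% in the other.

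**Effect on real versus sham.** Assume true rates of 30% and 15%, and *s* = 0.7 in both courses. The recorded rates are 21% and 10.5%. The ratio stays at 2.0, and the difference falls from 15 to 10.5 percentage points.

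**The case against.** A reader might infer that adverse effects will be under-counted, and most in the most impaired. The documents do not support that. They contain no data on how accurately people with PPA report symptoms, overall or by severity or variant. Participants must be able to take part in testing and therapy, sit through batteries of about three hours and complete a self-rated communication scale. Poor word retrieval does not show that someone cannot answer whether something hurts. This stands, so the direction is plausible rather than established.

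A reader might also infer that self-report is the only safety source. Sections 9.2, 9.7 and 12.2 show that it is not, although none describes another route for the subjective sensations.

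A third inference would be that the real-versus-sham safety comparison is biased or loses a known amount of power. Section 8.4.4 plans only an overall safety analysis: no test of real against sham, and none by severity or variant. Each participant has both courses with the order balanced, so equal under-reporting leaves the ratio unchanged. A power figure would describe an analysis that is not in the plan.

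Three further points are fair. The rates in 12.1 are themselves reported rates, so discounting them is illustration only. The CRF adverse-event module and the Daily tDCS Log are not reproduced, and either may already hold a symptom list. Section 12.1 regards these effects as minor. Even so, the protocol text should define how its primary safety endpoint is collected, and at present it describes a general question put to people with aphasia.

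**Conclusion.** The point holds as a measurement weakness with a cheap remedy. It does not invalidate the safety assessment. As written, the primary safety endpoint depends on participants' own answers, and no accessible format or proxy report is described for burning, itching or tingling, headache and pain. These may be under-recorded, possibly more in participants with greater impairment.

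The size is unknown. Recorded counts fall in proportion to *s*, by 10% to 50% over *s* = 0.9 to 0.5, and that range is an assumption. Absolute rates and differences would be too small. The real/sham ratio need not be biased, provided that reporting is equally complete in both courses. The protocol also leaves open whether findings under 9.2 and 9.7 count toward the endpoint in 3.2.3, and it gives three versions of when the question is asked.

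**What to change.** - In 3.2.3, 7.7 and 9.8.1, specify one fixed yes/no checklist of the five effects listed in 12.1 plus an item for anything else. Show it in words and pictures, and accept pointing or gesture as an answer. If the unseen log or CRF already has such a list, cite it and make it accessible.
- State one set of time points, identical in real and sham courses, and use it in all three sections.
- When a family member is present for the 9.7 question, also ask about discomfort they have seen or heard voiced. Record this source separately: a caregiver cannot feel tingling, so pooling the two would add little and blur the endpoint.
- State that findings under 9.2 and 9.7 count toward the safety endpoint.
- Do not add a routine staff check for redness. It could hint at the condition to blinded staff.

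The cost is a short form and a few minutes per session. The downside is that prompting will raise counts of mild events in both conditions, which the sham course helps to interpret. Because 12.2 attaches action to any reported effect, the authors should also say how checklist answers relate to that text.

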4.1 Inclusion Criteria

Study subjects must meet all of the following inclusion criteria:

- Presence of aphasia attributable to Primary Progressive Aphasia.
- Between the ages of 45 and 80.
- Must be a native English speaker

4.2 Exclusion Criteria

- Cognitive impairment of sufficient severity to preclude them from participating in testing / therapy (MMSE < 15).
- History of seizures or unexplained loss of consciousness in the past 6 months
- Subjects with metallic objects in the face or head other than dental apparatus such as braces, fillings, and implants.
- Subjects with Pacemakers or ICDs.
- Subjects with previous craniotomy or any breach in the skull; skull defect could be associated with shunting of current leading to unpredictable location and level of current affecting the brain.
- Subjects with a history of stroke
- Subjects with history of TIA (at the PI's discretion, a TIA which occurred at least 6 months ago is okay if no other events have been observed)
- Subjects with a history of small vessel disease
- Use of sedation medication that may cause arousing the subject during testing difficult (must be free of meds that impair cognition for at least 3 months)
- Pregnancy

CONFIDENTIAL

This material is the property of the University of Pennsylvania.

4.3 Subject

Individuals with Primary Progressive Aphasia will be recruited from two sources: 1) clinical practices at the Hospital of the University of Pennsylvania, 2) patients participating in [name] research cohort entitled "Neural Basis for Frontotemporal Degeneration" (IRB #298201). Additional participants may come from the Penn Memory Center (PMC) cohort and the VA Medical Center (VAMC) in Philadelphia. Potential participants' identified in clinical practice will be contacted directly by the relevant physician or a trained member of their staff. A trained research staff member will contact patients recruited from [name] on-going research project. We also will use the attached flyers to recruit patients around the University of Pennsylvania campus, Hospital of the University of Pennsylvania grounds, as well as on online FTD/PPA support groups and in-person support groups around the Philadelphia area. Finally, we will sometimes send an email script with information about the study to individuals who express an interest in learning more about the research study. Because this is a study of aphasia, a language disorder, oftentimes it is easier for participants to understand information if it is written down and they have time in advance to look things over. This email script will in no way replace the consent form or the consenting process, but we have found these scripts helpful in other studies.

4.4 Duration of Study Participation

The duration of the study as outlined above is approximately 12 months depending on how quickly the treatment sessions begin after baseline testing.

4.5 Total Number of Subjects and Sites

We intend to enroll up to 62 subjects: 31 naPPA/lvPPA; 31 svPPA

Subjects will be stimulated and tested in HUP or Perelman School of Medicine buildings. Depending on the availability of rooms, four testing sites may be employed: Neurology out-patient offices in the Perelman Center, Neurology out-patient offices on Ravdin 2, laboratory of [name] (Gibson 3), or laboratory of [name] (Goddard). The tDCS device is portable and no special equipment is required.

Additionally, if it is requested by the participant, we may conduct study sessions in the participant's home. In order to be eligible for home visits, patients must live within 40 miles, or approximately one hours, of the University of Pennsylvania. Ultimately, the discretion for eligibility of home visits will be up to the Principal Investigator, in order to best effectively and efficiently manage the lab's resources. If participants do qualify for home visits, they will be required to come to the lab for their first stimulation session. If the patient does not experience any adverse events during that stimulation session and if the other requirements are met, then all subsequent stimulation sessions would be conducted in the participant's home. Again, we would like to stress that this is only an option, not a requirement, which participants may choose if it is more convenient for them. Study visits not requiring the use of tDCS may be conducted at the participant's home if this situation proves to be more convenient for the participant.

4.6 Vulnerable Populations:

Children, fetuses, neonates, or prisoners are not included in this protocol.

Although not directly targeted, mentally disabled persons, economically or educationally disadvantaged persons, and/or employees or students of the University of Pennsylvania will not be denied enrollment and any special protections and/or additional safeguards will be undertaken

CONFIDENTIAL

in order to protect the rights and welfare of these subjects from coercion or undue influence as appropriate.

5 Study Intervention (Study drug, device, biologic, vaccine, food etc.)

5.1 Description

We will be using a commercially available tDCS devices manufactured by NeuroConn. This device is powered by rechargeable batteries and built-in blinding capabilities.

tDCS will be paired with simultaneous mCILT.

5.2 Intervention Regimen

tDCS will use two 5x5 electrodes, housed in saline soaked sponges, placed directly on the scalp. One electrode (anode) is placed over the targeted region of cortex (F7) and an electrode of opposite polarity (cathode) is placed over the left occipital cortex (O1). Stimulation will be administered at 1.5 mA in intensity and for 20 minutes per session. Sham stimulation will include a 30-second ramp-up and ramp down periods.

